The time point of the assessment of the primary and secondary outcomes is within 90 days after index surgery: SAES, PJI-likely, LOS, MACE, Hospital-treated infections (other than PJI and PJI-likely), Community-based antibiotic use, use of acetaminophen or non-steroidal anti-inflammatory drugs, and any revision after THA. The outcome of opioid use will be evaluated within 6 months before index surgery and within 90 days after index surgery.

STATISTICAL PRINCIPLES

Adherence and protocol deviations

This is a pragmatic randomized trial, applying the intention-to-treat (ITT) principle. The main analysis uses the treatment policy estimand, which quantifies the average treatment effect among all the centers who had undergone randomization, regardless of adherence to treatment or crossover (i.e., the intention-to-treat population). The ITT approach ensures that the results reflect real-world clinical practice, accounting for adherence variations and any protocol deviations (22). Deviations from the protocol and adherence will be monitored and documented during data management, but they will not exclude participants from the primary analysis.

Analysis populations

The primary analyses will be based on the ITT population based on the Full Analysis Set; i.e., all patient's undergoing the prespecified surgery using the antibiotic dose corresponding to the specific cluster and year (cross-over, cluster randomization) (22). Accordingly, participants allocated to a treatment group ($X_{\text{Single-dose}}$ and $X_{\text{Multiple-dose}}$, respectively) will be followed up, assessed, and analyzed as members of that cluster, irrespective of the actual antibiotic regimen used in the specific clinic (i.e., independent of physicians' withdrawals and cross-over phenomena) (23, 24).

TRIAL POPULATION

Screening data

The total number of patients enrolled during the trial period of 2 years, will be collected and reported according to CONSORT flowchart (see **Figure 1**, Mockup below). Furthermore, the

number of ineligible patients including reason for ineligibility and patients with loss to follow-up will be reported.

Eligibility

All patients \geq 18 years receiving a primary THA conforming to the following inclusion and exclusion criteria are considered eligible for the trial.

Inclusion Criteria:

1. primary and secondary causes of osteoarthritis

Exclusion Criteria:

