Community-based antibiotic use (any community-treated infection or antibiotic use after discharge) is defined as at least one dispensing after discharge from index THA surgery and broad-spectrum antibiotics based on the Anatomical Therapeutic Chemical classification (ATC) codes. All antibiotics in Denmark require prescriptions from a physician. The Danish National Health Service Prescription Database has registered all reimbursed prescriptions from all community pharmacies since 2004. Medications are coded according to the ATC codes listed in Appendix B. All antibiotics in Denmark require prescriptions from a physician and these will be identified using NPR (41). We aim to specifically examine the redemption of ATC code J01E prescriptions within one week following the index operation to capture instances of post-operative urinary tract infections.

7) Opioid use

Patients who received at least one opioid prescription following primary THA surgery. All opioids in Denmark require prescriptions from a physician and these will be identified using NPR (41). The following ATC codes (including all subcodes) are included: N01AH (opioid anesthetics), N02A (opioids), N07BC02 (methadone), and R05DA04 (codeine). Given the lack of a clear definition for opioid users, we defined opioid users as patients who redeemed two opioid prescriptions within six months prior to THA surgery. Conversely, patients who did not redeem two or more opioid prescriptions within this timeframe were classified as opioid naïve. For opioid naïve patients, opioid use post-THA is defined as the redemption of two opioid prescriptions within 90 days following surgery. We assert that two separate redeemed prescriptions confirm actual medication use. We will calculate the treatment dosage based on the number of packages and volume redeemed within 90 days post-surgery. To investigate dosages, all doses will be converted to morphine milligram equivalents using a conversion factor specific to the type of opioid (42, 43).

8) Use of acetaminophen or non-steroidal anti-inflammatory drugs

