The primary analyses will be based on the Intention to Treat (ITT) population, i.e., all patients undergoing the prespecified surgery corresponding to the specific year (cross-over, cluster randomization). Two-sided 95% confidence intervals will be estimated and reported enabling (standard) superiority interpretations. The primary statistical analysis model will be based on a *Generalized Linear Mixed Model*, with a random effects factor applied indexing the clinical center (36 levels: 1, 2, 3, ..., up to 36), a fixed effect will be applied for period (2 levels: 1st and 2nd year, respectively), and antibiotics group (2 levels: Single-dose and Multiple-dose, respectively), as well as the interaction between the two period and antibiotics group (period×group; 4 levels: 2×2 levels). For the primary endpoint: Noninferiority will be shown if the upper limit of the two-sided 95% CI for the odds ratio is less than 1.4 for the single antibiotic doses as compared with multiple doses.

In addition, subgroup analyses will be performed to examine the following known and suspected baseline risk factors for PJI infection will be compared: age (≥ 65 versus < 65 years), sex (male versus female), Anthropometric categories (BMI: ≥ 30 versus $< 30 \text{ kg/m}^2$) as well as morbid obesity (BMI: ≥ 40), and presence of diabetes (with versus without). Additional analyses of the study will assess whether the difference of PJI risk in the two treatment arms differ in specific subsets of patients: femoral stem cementation (antibiotic-loaded bone cement versus bone cement with no antibiotic-load and cementless fixation vs fixation with bone cement) and type of antibiotic (beta-lactam antibiotics versus other). The rationale for these analyses is that we suspect the risk of infection to be different in these subgroups. The pharmacokinetics of the antibiotics might have an impact on the infection rates in the relevant groups. The statistical approach for this evaluation of potential effect modifiers is a test for statistical interaction to evaluate whether the treatment effect varies across levels of the effect modifier (46).

Finally, blinded results from the statistical analyses (single-dose compared to multiple-dose) will be presented to the author group followed by development of two written interpretations. The author group will sign a consensus statement comprising both interpretations prior to the unsealing of the randomization code.(47)

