Missing data and sensitivity analyses

The main analyses will be based on the data as it appears in the database. Consequently, missing data is handled according to a Missing Completely At Random (MCAR) assumption (48). Conducting sensitivity analyses in a randomized trial assessing the risk of PJs following a single-dose versus multiple-dose antibiotic prophylaxis is essential to ensure the robustness and credibility of the findings. To evaluate the consistency of the primary endpoint and some or all the key secondary endpoints across various assumptions, missing data will be imputed using best-case, worst-case, best-worst-case, and worst-best-case imputations (49, 50) the results will be combined using Rubin's rule.

Additional analyses

Stratified analysis

In secondary analyses, important contextual factors for a binary endpoint will be examined using statistical interaction tests, as proposed by Christensen et al. (46). Known and suspected baseline risk factors for PJI will be evaluated as potential effect modifiers: age group (<65 vs \geq 65 years), sex (male vs female), anthropometric category (BMI: <30 vs \geq 30 vs $>$ 35 kg/m²) and presence of diabetes (with vs without). Additional analyses of the study will assess whether the difference of PJI risk in the two treatment arms differ in specific subsets of patients: femoral stem cementation (antibiotic-loaded bone cement vs bone cement with no antibiotic-load and cementless fixation vs fixation with bone cement) and type of antibiotic (beta-lactam antibiotics vs other). The rationale for these analyses is that we suspect the risk of infection to be different in these subgroups. The pharmacokinetics of the antibiotics might have an impact on the infection rates in the relevant groups. The statistical approach for this evaluation of potential effect modifiers is a test for statistical interaction to evaluate whether the treatment effect varies across levels of the effect modifier (46). The subgroup analyses will be presented as demonstrated in Mock-up Figure 3A and B. No additional analyses on the primary and key secondary outcomes are planned from baseline to 90-day follow-up.

Harms

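### The opioid comparison does not adjust for the pre-operative opioid status that the SAP itself derives, and its single results row has two competing definitions

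*SAP*

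**What the plan says.** Under Timing of secondary outcome assessments, the SAP states: "The outcome of opioid use will be evaluated within 6 months before index surgery and within 90 days after index surgery". Item 7 of the key secondary endpoints explains the look-back: "we defined opioid users as patients who redeemed two opioid prescriptions within six months prior to THA surgery". All other patients are classed as naive. The source is the national prescription registry: "All opioids in Denmark require prescriptions from a physician and these will be identified using NPR".

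The same item gives two post-operative definitions. It opens with "Patients who received at least one opioid prescription following primary THA surgery" and later states: "For opioid naïve patients, opioid use post-THA is defined as the redemption of two opioid prescriptions within 90 days following surgery". Table 2 has one opioid row, in a table titled for the intention-to-treat population.

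The model under Analysis methods, repeated in the footnote to Table 2, is a GLMM "with a random effects factor applied indexing the clinical center". In addition, "a fixed effect will be applied for period (2 levels: 1st and 2nd year, respectively), and antibiotics group", together with their interaction. It contains no patient-level covariate. Prior opioid use is not in the list of baseline characteristics, in Table 1 or among the effect modifiers. The section on stratified analysis ends: "No additional analyses on the primary and key secondary outcomes are planned from baseline to 90-day follow-up".

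**The concern.** Redemptions before surgery cannot respond to the antibiotic regimen, so they are a baseline value. They are the same kind of measurement as the outcome, from the same registry, and are probably strongly prognostic. The SAP treats them as important enough to classify patients, then does not use the classification in the model or display it.

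The design gives this some weight. The randomised units are 36 centres, each contributing two one-year blocks. The centre effect absorbs stable differences between centres, and the period effect absorbs a trend common to all of them. Neither absorbs a change in the share of prior users that is specific to one centre between its two years, and the model has no centre-by-year term. The SAP expects patient characteristics to be stable between years, but a reader could not check that for prior opioid use.

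The definition is also open. The row could be analysed in all patients with one prescription as the event, in all patients with two, in naive patients only, or with a rule that differs by prior status. These give different percentages and differ in how far they depend on prior use.

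**Working it through.** The SAP gives no opioid rate, effect size or precision, so there is no figure of its own to reproduce. From the SAP: up to 10,000 patients per group, 36 centres, two years, two-sided 5% level. Assumed: prior use q = 20% on average, and post-operative rates in users and naive patients (pU/pN) of 60%/15% and 80%/15% for two redemptions and 95%/65% for one prescription.

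**1. Precision with no centre-year variation (60%/15%)**
- Overall rate: p = 0.20 × 0.60 + 0.80 × 0.15 = 0.24.
- Unadjusted variance per patient: 0.24 × 0.76 = 0.1824. SD of the group difference: √(2 × 0.1824 / 10,000) = 0.60 points.
- Variance within prior-use strata: 0.20 × 0.60 × 0.40 + 0.80 × 0.15 × 0.85 = 0.150. SD: √(2 × 0.150 / 10,000) = 0.55 points.
- Simulation gave 0.60 and 0.54. For 80%/15% it gave 0.64 and 0.52, and for 95%/65% it gave 0.65 and 0.63.

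**2. Type I error with centre-specific changes between years**

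The simulation had no treatment effect, 36 unequal centres, 20,000 patients and 4,000 runs per setting. It used a linear probability model with centre, period and group as fixed effects, as a simple stand-in for the GLMM. The interaction was left out.

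| Centre-year SD of prior use (points) | 60%/15% | 80%/15% | 95%/65% |
|---|---|---|---|
| 0 | 4.3% | 5.1% | 5.1% |
| 1 | 5.2% | 6.1% | 5.4% |
| 2 | 7.2% | 9.6% | 6.0% |
| 3 | 9.7% | 12.8% | 6.6% |
| 5 | 17.6% | 24.3% | 10.5% |

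With prior use in the model, the error was 4.5 to 5.4% in every setting. In naive patients only, it was 4.4 to 5.7%. A 3-point rise common to all centres left the unadjusted error at 5.6%, because the period effect absorbs it. The Monte Carlo standard error near 5% is √(0.05 × 0.95 / 4,000) = 0.34 points.

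**3. Hand check with equal centres (60%/15%)**
- At a centre-year SD of 2 points, the extra SD of the arm difference in prior use is 2 × √(2/36) = 0.471 points. Multiplied by the 0.45 gap in rates, this adds 0.212 points to the outcome difference.
- True SD: √(0.604² + 0.212²) = 0.640. The nominal threshold becomes 1.96 × 0.604 / 0.640 = 1.85, which gives an error of 6.4%.
- At 3 points the same steps give 0.707 × 0.45 = 0.318, a true SD of 0.683 and an error of about 8.3%.
- Unequal centre sizes in the simulation raise these to 7.2% and 9.7%.

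**4. Effect of the open definition**

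Under the same assumed rates (60%/15% for two redemptions, 95%/65% for one prescription), the row would show:
- two redemptions, all patients: 24%
- one prescription, all patients: 0.20 × 0.95 + 0.80 × 0.65 = 71%
- two redemptions, naive patients only: 15%
- one prescription for users and two for naive patients: 0.20 × 0.95 + 0.80 × 0.15 = 31%. The gap between strata is then 80 points, wider than any gap simulated.

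**The case against.** A reader might infer that a small shift in prior use at a centre can pass as a treatment effect. One could support this as follows: with 20% prior use and rates of 70%/25%, a 2-point difference between whole arms moves the log odds ratio by 0.040 against a standard error of 0.030, so z = 1.34 and the chance of a false significant result is 27%. The arithmetic is right, but the figure applies only once that arm-wide imbalance has occurred. The chance SD of the arm difference in prior use is √(2 × 0.20 × 0.80 / 10,000) = 0.57 points, so 2 points is about 3.5 SD. A shift at one of 36 equal centres is diluted 36-fold, and shifts cancel unless they line up with allocation. The 27% is not the trial's error rate and should not be used.

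A reader might also infer from the timing sentence that pre-operative redemptions count as outcome events. Item 7 does not support that, because it defines use by prescriptions after surgery. The timing sentence is only loosely worded.

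Three further objections have force.
- Randomisation keeps the unadjusted comparison unbiased on average, and with no centre-year variation its error is about 5%.
- The excess error arises from centre-by-year variation that the model does not represent, and prior opioid use is one route for it.
- If the row is meant for naive patients only, the exposure largely disappears. The SAP does not say so, and Table 2 is titled for the intention-to-treat population.

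Finally, this is one of nine key secondary outcomes, which the SAP says it will interpret with caution.

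**Conclusion.** The point holds as a missed adjustment and an unresolved definition. It does not show that the opioid result will be biased. Under assumed rates of 60%/15%, adjustment lowers the SD of the group difference from 0.60 to 0.54 percentage points. At an assumed centre-year SD of 2 to 3 points, the unadjusted type I error is about 6 to 10% (6.0 to 9.7% for the 95%/65% and 60%/15% pairs, 9.6 to 12.8% for 80%/15%), against about 5% with adjustment. All opioid rates and the centre-year SD are assumptions, and the simulation is on the risk-difference scale with a simplified model.

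The conflict between one and two prescriptions, and the unstated population for the row, can be read directly from the SAP and need no assumption. Neither matter affects the primary endpoint. The change is worth making because it costs almost nothing.

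**What to change.** - State one post-operative definition and one analysis population for the opioid row in Table 2, counting redemptions from surgery to day 90 only. Reword the timing sentence so that the six months before surgery is named as a baseline window.
- Add pre-operative opioid status (user or naive) as a fixed effect in the GLMM for this outcome, and report the unadjusted odds ratio alongside. The two odds ratios are not the same quantity, because an odds ratio changes when a prognostic covariate is added. The absolute risk difference should therefore come from risks standardised over prior status. Applying the adjusted odds ratio to the crude reference risk would not give it.
- Show pre-operative opioid status by group in Table 1.
- Do the same for acetaminophen and NSAIDs, where item 8 defines users from the six months before surgery and the model again does not use the status.

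The cost is a few sentences in the SAP, one row per drug class in Table 1 and a little extra analysis. The pre-operative redemptions must already be extracted for the classification, so no new data are needed.

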1. Patients receiving a primary THA due to either acute or sequelae of proximal femoral or acetabular fractures
2. Patients receiving a primary THA due to bone tumor or metastasis

Primary and secondary causes of osteoarthritis include: primary idiopathic arthritis, congenital hip dislocation, Morbus Calvé-Legg-Perthes, epiphysiolysis, dysplasia of the acetabulum, atraumatic caput necrosis, rheumatoid arthritis, Morbus Bechterew, other or other arthritis. Concerning developmental dysplasia, approximately 3% of the patients will have secondary OA due to acetabular dysplasia and 2% due to femoral head necrosis (25).

Recruitment

The CONSORT flowchart will comprise number of patients screened, excluded (with reasons) eligible for inclusion in the trial, randomized, receiving their allocated treatment and lost to follow-up (with reasons), included in ITT analysis. The CONSORT flowchart is depicted in Mockup Figure 1.

Follow-up

Follow-up are planned based on routine treatment practice and registration in administrative national validated databases and registries. Therefore, participation will not result in additional hospital visits.

Timing of loss to follow-up will be presented in the CONSORT flowchart with numbers and reasons for loss to follow-up given at the 90 days (primary end point) outcome

assessment. Furthermore, the number (with reasons) of loss to follow-up during the course of the trial will be summarized by treatment group.

Baseline patient characteristics

The following data will be obtained from the patient at baseline: sex, age, height, weight, Body-mass index, American Society of Anesthesiologists classification (ASA), Comorbidity status, socioeconomic status (SES), whether the patient has diabetes (ICD-10 codes E10-E14 from DNPR), year of surgery, antibiotic agent applied as prophylaxis, duration of surgery, type of fixation, type of prosthesis and type of operating room as elaborated in Mockup **Table 1**.

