Comorbidity status will be evaluated using the Charlson Comorbidity index Score (CCI) (26). Information about comorbidities will be collected from DNPR (27, 28) after linkage using CRS(29) (27). The CCI score will be calculated based on all primary and secondary diagnoses from hospitalizations and outpatient visits registered as ICD-10 codes in the DNPR over a 10-year period before the primary THA. Although the positive predictive value (PPV) for diagnosis and treatment varies substantially in the DNPR (27), the overall PPV for the 19 Charlson conditions has been found to be 98.0% (30). For each patient that undergoes surgery during the trial period, information on SES will be based on retrieved information on marital status, cohabitation, highest obtained level of education, occupation, family income, and a measure of family liquid assets on the index date retrieved from Statistics Denmark (31). SES will be categorized into the following three domains: educational level, income, and employment status. Educational level will be categorized as low, medium, or high. Low includes no education or high school completed, medium includes vocational education or higher preparatory programs, and high includes a bachelor's or higher degree. Cohabitation status will be classified as living alone, cohabiting, or other. Cohabitation status will be classified as living alone or cohabiting with an adult partner (married, unmarried, or living in multifamily housing). Wealth will be determined using either family income (total in a co-housing family before taxes) or family liquid assets (including cash property value, bank deposits, and securities such as stocks, bonds, and mortgage deeds), depending on the patient's age. For patients aged ≥ 65 years, the standard retirement age in Denmark, family liquid assets will be used, as income may no longer accurately reflect financial status. For patients aged < 65 years, family income will be used. Family income at the time of THA is calculated as the average annual pre-tax income in kroner (1 Euro \approx 7.5 Kroner) over the 5 years prior to surgery. Income is classified as above or below the mean for each age group (0-59, 60-69, 70-79, 80+). To account for annual

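### Diabetes, a prespecified effect modifier, is identified from DNPR diagnosis codes only, so patients never coded at a hospital or outpatient contact count as non-diabetic although the linked prescription registry could identify many of them

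*SAP*

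**What the plan says.** Under Baseline patient characteristics, the SAP lists "whether the patient has diabetes (ICD-10 codes E10-E14 from DNPR") among the baseline variables. It adds no prescription code and gives no look-back period for diabetes.

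The next paragraph of that section describes the DNPR data used for the Charlson index as "all primary and secondary diagnoses from hospitalizations and outpatient visits registered as ICD-10 codes in the DNPR over a 10-year period" before surgery. In support of the codes it says that "the overall PPV for the 19 Charlson conditions has been found to be 98.0"%. It gives no sensitivity.

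Diabetes is not only a Table 1 descriptor. Analysis methods lists "presence of diabetes (with versus without") among the subgroups for PJI, and Stratified analysis repeats "presence of diabetes (with vs without"). The stated method is "a test for statistical interaction to evaluate whether the treatment effect varies across levels of the effect modifier".

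The prescription registry (NPR) already serves four outcomes in the text and in Appendix B: PJI-likely, community antibiotic use, opioid use, and acetaminophen/NSAID use. For opioids and for acetaminophen/NSAIDs it is also read for the six months before surgery. On opioids the SAP says: "We assert that two separate redeemed prescriptions confirm actual medication use".

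**The concern.** As the SAP describes it, the DNPR holds diagnoses made at hospital and outpatient contacts. Diabetes that was never coded at such a contact is invisible to this definition, and the patient falls into the group without diabetes.

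The PPV does not settle the matter. It tells us that a coded case is very probably real. It does not tell us how many real cases carry no code, and that is the quantity at issue here.

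At stake is one secondary analysis. The SAP treats diabetes as a known or suspected risk factor for PJI and asks whether the effect of a single dose differs in these patients. PJI is rare, so the diabetes stratum will hold few events even with perfect ascertainment. Missed cases remove events from the smaller stratum, which determines most of the precision of the interaction test. They also move some patients with diabetes into the comparison stratum, which pulls the two odds ratios (ORs) together when the effect truly differs.

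**Working it through.** **No figure to reproduce.** The SAP gives no diabetes prevalence, subgroup size, code sensitivity or interaction power. What follows is illustrative.

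**Inputs from the SAP** (Sample size and power calculation): about 20,000 patients and a mean PJI rate of 1.2%, hence 20,000 × 0.012 = 240 PJIs.

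**Assumptions, not in the SAP:** true diabetes prevalence 10%; DNPR codes capture 100, 80, 65 or 50% of cases; every coded case is real; PJI risk in diabetes is either double or equal to that in other patients; clustering is ignored.

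**Step 1, events in the diabetes stratum.**
- Doubled risk: diabetes supplies 0.10 × 2 / (0.90 + 0.10 × 2) = 0.182 of events, so e = 240 × 0.182 × capture.
- Equal risk: e = 240 × 0.10 × capture.

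**Step 2, detectable ratio of ORs.** With events split evenly between arms, the variance of the log OR in a stratum with e events is about 4/e. So SE = sqrt(4/e + 4/(240 − e)), and the ratio detectable with 80% power at two-sided 5% is exp(2.8 × SE), where 2.8 = 1.96 + 0.84.

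| Capture | Events (doubled risk) | SE | Detectable ratio | Events (equal risk) | SE | Detectable ratio |
|---|---|---|---|---|---|---|
| 100% | 43.6 | 0.335 | 2.6 | 24.0 | 0.430 | 3.3 |
| 80% | 34.9 | 0.366 | 2.8 | 19.2 | 0.476 | 3.8 |
| 65% | 28.4 | 0.400 | 3.1 | 15.6 | 0.524 | 4.3 |
| 50% | 21.8 | 0.449 | 3.5 | 12.0 | 0.592 | 5.3 |

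**Step 3, contamination of the stratum without diabetes at 50% capture.**
- Missed cases are 0.05/0.95 = 5.3% of its patients.
- Doubled risk: they supply (0.05 × 2)/(0.90 + 0.05 × 2) = 10% of its control-arm events. With a true OR of 2.0 in diabetes and 1.0 otherwise, the OR in this stratum becomes about 0.9 × 1.0 + 0.1 × 2.0 = 1.1. The ratio of ORs is then 2.0/1.1 = 1.82.
- Equal risk: they supply 5.3% of events, and the ratio is 2.0/1.053 = 1.90.

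**Step 4, a second set of assumptions.** Take 10,000 per group, control PJI risk 1.0%, prevalence 12%, PJI risk ratio 1.5 for diabetes, and ORs of 2.0 (diabetes) and 1.0 (others). A Wald test on the difference in log ORs has 53% power at full capture, 37% at 70% and 27% at 50%. The expected ratio of ORs goes from 2.00 to 1.89 to 1.83. With a true OR of 1 in diabetes, the 95% limits in that stratum widen from 0.51–1.97 at full capture to 0.44–2.25 at 70%.

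Both sets agree: the attenuation is mild, and the main cost is lost precision.

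**The case against.** The definition is clear, reproducible and taken from the same registry as the Charlson index. It contradicts nothing in the SAP. The figure that would decide how much it matters, the share of diabetes that the DNPR misses, is not in the document, and full capture cannot be excluded. The Figure 3 legend already warns against definitive conclusions from subgroup intervals. Even full capture does not give 80% power for a ratio of 2.0. A prescription rule brings errors of its own, because redeeming a drug is evidence of use and not of the disease. All of this stands, and it makes the point an improvement and not an error in the plan.

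A reader might infer three stronger things that the document does not support.
- **That every patient managed outside hospital is missed.** A secondary diagnosis at any hospital or outpatient contact would count, and every trial patient has at least the contact for the hip operation. Only patients never coded are missed.
- **That the diabetes subgroup is diluted.** If the cited PPV applies to diabetes, its members are nearly all true cases and the OR within it is essentially unbiased. The contamination falls on the much larger other stratum.
- **That the main result is affected.** Diabetes status does not enter the primary model.

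What the objection does not answer is that the evidence offered for the codes concerns false positives only, while a second source is already linked and already read before surgery.

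**Conclusion.** The point holds as a low-cost improvement to one prespecified subgroup analysis. Defining diabetes by E10–E14 codes alone makes the diabetes stratum smaller than it need be, by an amount the SAP does not let us determine, and slightly contaminates the stratum without diabetes.

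If half the cases were missed, with 10% prevalence and 240 PJIs, the diabetes stratum would lose half its events: about 44 to 22 with doubled PJI risk, or 24 to 12 with equal risk. The ratio of ORs detectable with 80% power would rise from about 2.6 to 3.5, or from 3.3 to 5.3. A true ratio of 2.0 would appear as about 1.8, or 1.9. Better capture would make the loss proportionately smaller. Prevalence, capture and relative risk are all assumptions.

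**What to change.** Before the randomization code is unsealed, define diabetes as either of:
- an E10–E14 code in the DNPR in the 10 years before surgery, the look-back already used for the Charlson index; or
- at least two redemptions of glucose-lowering drugs (ATC A10) in the NPR in the 12 months before surgery. A class also used for weight loss should not count on its own, and the codes concerned should be listed in Appendix B.

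Use this definition in Table 1 and in the interaction test. Repeat the interaction test with the DNPR-only definition as a sensitivity analysis, and report how many patients each source contributes.

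The cost is one more ATC group to extract and a pre-operative window of 12 months, where the SAP now reads six. The SAP does not say whether the present extract could simply be extended. A few false positives will enter through redemptions for other indications. They would fall in the small diabetes stratum, which is why the rule asks for two redemptions, excludes the weight-loss class on its own, and keeps the DNPR-only analysis alongside.
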